## 5.3 Secondary endpoints

The main analyses of the secondary endpoints will contrast the randomized groups at 24 months (analyses using additional time points are specified in Section 5.8).

### 5.3.1 Adverse events and complications

The following adverse events will be collected:

- Surgical site infections
- Neurological sequel in both groups
- Thromboembolic disease
- Re-rupture in surgical treated patients

Adverse events (AEs) will be summarized in tables by arm. If justified based on the number of AEs in each arm, we may also analyze the safety endpoints in two different ways: (1) Any AE using a logistic regression model with arm allocation as the main contrast, adjusted for site, age, sex, and degree of tendon retraction; (2) Total number of AE using Poisson regression with arm allocation as the main contrast, adjusted for site, age, sex, and degree of tendon retraction.

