#### 4.2.2.1 Adverse events and complications (both groups)

- Surgical site infections (surgery group only)
- Neurological sequel
- Thromboembolic disease
- Re-rupture in surgically treated patients
- Other complications and reoperations

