# 5 Analysis of the trial

## 5.1 Analysis populations

The *intention to treat (ITT) population* will consist of all participants randomized and consenting to be part of the study, irrespective of treatment received. Participants in the ITT population will be analyzed according to the treatment they are randomized to, regardless of whether they actually received this treatment or not.

We will also conduct *per-protocol (PP)* and *as-treated (AS)* analyses. Cases will be considered treatment crossovers if the randomly assigned treatment is changed. Non-operative treated patients who are treated operatively due to late complaints (>3 months after inclusion) will in PP and AS analyses be handled in two ways: (i) *not* considered crossovers, in which case we regard these sets of patients as a failed initial conservative treatment strategy, followed by surgery; (ii) considered as cross-overs (analogously to patients who switch groups early, i.e. within 3 months of randomization). The first definition will be employed in the main PP and AS analyzes, whereas the latter will be used in sensitivity analyses (see Section 5.8.4).

The *per protocol (PP) population* will be defined by the participants who were randomized to a specific treatment and received it according to the protocol. Analyses based on the PP population are based on post randomization events (treatment compliance vs. not), which may lead to biased results. We will therefore perform analyses on the PP population using inverse probability weighting to adjust for the effect of these post randomization events. Specifically, let  $A$  be an indicator variable that takes value 1 if the patient was randomized to the surgical arm and 0 if s/he was randomized to the conservative treatment arm. The conditional probability of adhering to the protocol given study arm and other covariates is  $Pr(P=1|Z,A)$ , where  $Z$  is patient covariates (age, sex, site, and degree of tendon retraction). Inverse probability weights of protocol adherence will be defined as  $W=1/Pr(P=1|Z,A)$ . The weights  $W$  will then be used to estimate the contrasts between the operative and non-operative arms using marginal models with a robust (sandwich) standard error estimator according to models specified in Sections 5.2 and 5.3.

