The *as treated (AS) population* will be defined according to the treatment the patients actually received. Analogously to the PP population, the definition of the AS population is based on post randomization events, which may lead to biased results. We will therefore conduct analyses on the AS population by first identifying subgroups that are likely to require surgery and therefore should not be considered as good candidates for conservative treatment, and then contrast the outcomes of patients treated successfully in the conservative treatment arm with patients randomized to the surgery arm who similarly would not have crossed over had they been randomized to the conservative treatment arm. We will within the trial observe which patients in the conservative management arm who cross over. However, patients cannot cross over from the surgical to the conservative arm, after the surgery is performed. We will use matching based on inverse probability weighting (as defined above for the PP population) to identify a comparison group from the surgical arm for compliers in the conservative management arm.

The number and proportion of patients who did not receive the treatment they were allocated to will be reported. If any other trial treatment options were known to be received, instead of or in addition to, the allocated treatment during the follow-up period after the first randomization, these will be collected and reported.

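### Adverse events are analysed only by allocated arm, so no specified analysis pools the surgical complications of all patients who were operated on

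*SAP*

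**What the plan says.** Section 5.3.1 sets the tabulation: "Adverse events (AEs) will be summarized in tables by arm". If event numbers justify it, two models may follow: "Any AE using a logistic regression model with arm allocation as the main contrast", and "Total number of AE using Poisson regression with arm allocation as the main contrast". Section 5.3 gives the general rule: "The main analyses of the secondary endpoints will contrast the randomized groups at 24 months".

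Section 5.1 defines three analyses.
- **ITT:** participants "will be analyzed according to the treatment they are randomized to, regardless of whether they actually received this treatment or not".
- **PP:** patients who received their assigned treatment, weighted for adherence, using the models of Sections 5.2 and 5.3. Conservative-arm surgery after 3 months is not a cross-over in the main PP and AS analyses (definition i). It is a cross-over in the sensitivity version (definition ii).
- **AS:** introduced as following treatment received, but the analysis then described is to "contrast the outcomes of patients treated successfully in the conservative treatment arm with patients randomized to the surgery arm" who would likewise not have crossed over.

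Section 6.1 says that cross-over was expected.

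In Section 4.2.2.1 two items are tied to surgery: "Surgical site infections (surgery group only" and "Re-rupture in surgically treated patients". Section 5.3.1 lists infections without the restriction and keeps it for re-rupture.

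**The concern.** Avoided surgical harm is a main reason to accept a non-operative treatment that is only non-inferior on PHAT. Readers will therefore want to know how often the operation causes an infection, a nerve injury or another complication, and whether delayed surgery differs from early surgery. The plan foresees operations in the conservative arm but has no safety summary whose denominator is everyone operated on.

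The denominators for the surgery-specific events are also unsettled. The term used for infections in Section 4.2.2.1 does not say whether the surgery group is the allocated or the operated one. Under a by-arm table, surgical-arm patients who never had the operation stay in the denominator for infection although they cannot have the event. Infections after cross-over surgery have no clear place.

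**Working it through.** **Step 1. Where a surgical complication in an operated conservative-arm patient goes.** This follows from the definitions in Section 5.1.

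| Analysis | Surgery within 3 months | Surgery after 3 months |
|---|---|---|
| ITT | conservative arm | conservative arm |
| PP, definition (i) | excluded | conservative arm |
| PP, definition (ii) | excluded | excluded |
| AS as specified, (i) | excluded as a non-complier | conservative if counted as a complier; excluded if not regarded as a treatment success |
| AS as specified, (ii) | excluded | excluded |

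In no cell does the event join the operated side.

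**Step 2. Dilution of the ITT contrast, read as a measure of harm from the operation.** The plan has no figure of its own to reproduce. The 60 per arm comes from Section 6.2. Everything else is assumed, because the SAP gives no cross-over or complication rate: risk 0.10 if operated and 0.03 if not (RR 0.30, difference 7.0 points), with e early and l late operations in the conservative arm and s surgical-arm patients not operated on.

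- Surgical arm: [(60 − s)·0.10 + s·0.03]/60
- Conservative arm: [(e + l)·0.10 + (60 − e − l)·0.03]/60
- Share of operated patients in the conservative arm: (e + l)/(60 − s + e + l)

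| e / l / s | Surgical arm | Conservative arm | RR | Difference (points) | Share |
|---|---|---|---|---|---|
| 3 / 2 / 2 | 5.86/60 = 9.77% | 2.15/60 = 3.58% | 0.37 | 6.2 | 5/63 = 8% |
| 6 / 3 / 3 | 5.79/60 = 9.65% | 2.43/60 = 4.05% | 0.42 | 5.6 | 9/66 = 14% |
| 10 / 5 / 5 | 5.65/60 = 9.42% | 2.85/60 = 4.75% | 0.50 | 4.7 | 15/70 = 21% |

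The difference equals 7.0 × [1 − (e + l + s)/60], so its proportional shrinkage does not depend on the risks chosen. A simpler case shows the range: no background risk, the whole surgical arm operated on, a share c of the conservative arm operated on, and risk p per operation. The by-arm difference is then p(1 − c). At p = 10% and c = 5%, 10%, 20%, 30% it is 9.5, 9.0, 8.0 and 7.0 points. Over the same c it runs from 4.75 to 3.5 points at p = 5%, and from 19 to 14 points at p = 20%.

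**Step 3. The same cases under PP, unweighted.** The surgical arm contains only operated patients, so its risk is 10%. Under definition (i) the conservative arm is [l·0.10 + (60 − e − l)·0.03]/(60 − e).

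| e / l / s | Conservative arm, (i) | RR | Difference (points) |
|---|---|---|---|
| 3 / 2 / 2 | 1.85/57 = 3.25% | 0.325 | 6.8 |
| 6 / 3 / 3 | 1.83/54 = 3.39% | 0.339 | 6.6 |
| 10 / 5 / 5 | 1.85/50 = 3.70% | 0.37 | 6.3 |

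Under definition (ii) the conservative arm is 3%, which returns RR 0.30 and 7.0 points. This assumes that late operations carry the same risk as early ones; the PP analysis could not test that.

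**Step 4. Scale.** The standard error of the difference at 60 per arm is √(0.10·0.90/60 + 0.03·0.97/60) = 0.045, or about 4.5 points. The ITT shift in Step 2 is 7.0 − 6.2 = 0.8 to 7.0 − 4.7 = 2.3 points.

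**The case against.** Much of the defence stands.

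- A reader might infer that by-arm counting puts complications on the wrong side. The SAP does not support that. Counting by allocation is the declared ITT rule, and Section 5.1 treats late surgery as failure of the conservative strategy. Harm that follows belongs to that strategy.
- A reader might infer that the plan never yields the complication risk of the operation. It can: PP extends to the Section 5.3 models, and Step 3 shows little or no dilution there.
- A reader might infer that AS leaves every operated conservative-arm patient out of both groups. For late surgery under definition (i) they may stay on the conservative side. Read literally, the opening AS sentence would even group patients by treatment received. The difficulty is that this sentence and the analysis after it do not agree.
- A reader might infer that infections after cross-over surgery go uncounted. That needs the allocated-group reading of one phrase. The Section 4.2.2.1 heading covers both groups, and Section 5.3.1 has no such limit. Re-rupture is already restricted to surgically treated patients in both places.
- Section 5.1 promises counts of patients not receiving their allocation and of other treatments received, and Section 7.1 words its relative risk as if everyone had been treated one way or the other. But the counts carry no complications with them. Section 7.1 says that it compares the two arms and does not say that its treatment covariate is treatment received.
- The shift is small beside the standard error, and the rates are assumed.

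What the defence does not answer is that the PP surgical arm omits every operation in the conservative arm, and with them all information on delayed surgery.

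**Conclusion.** The gap is real but limited. Adverse events are tabulated and modelled by allocated arm, operations in the conservative arm are foreseen, and no analysis as specified pools all operated patients. The ITT comparison is valid for the strategies. As a measure of what the operation itself does, it is diluted to RR 0.37 to 0.50 against 0.30 under the assumed 10% and 3% risks and the three adherence patterns shown. PP largely removes the dilution on the same assumptions, so the documents do not support a claim that the operation's risk is unobtainable. What is lost is the 8% to 21% of operated patients who sit in the conservative arm in those examples, and any view of complications after delayed surgery. The direction holds whenever operated patients have the higher risk; the size cannot be fixed from the SAP. Separately, the surgery group in the infection item is undefined, and Section 4.2.2.1 differs from Section 5.3.1. This is a low-cost improvement to safety reporting and does not invalidate the randomized comparison.

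**What to change.** 1. Keep the by-arm table in Section 5.3.1 as the randomized comparison.
2. Add one unweighted descriptive table by treatment received, labelled non-randomized. The operated group is every randomized patient operated on at any time, in either arm, counting events on or after surgery. Patients operated on more than 3 months after inclusion get a separate row with follow-up since surgery. The other group is patients never operated on. Events that precede a later operation are listed separately, so no patient is in both denominators.
3. In Sections 4.2.2.1 and 5.3.1, use patients operated on, in either arm, as the denominator for surgical site infection and re-rupture.
4. Reconcile the opening AS definition in Section 5.1 with the analysis that follows it.

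The cost is SAP wording and one table. Section 5.1 already has treatments received collected; the table also needs dates of surgery and of events, which I assume are held. The downside is a table that is not a randomized comparison. Because the SAP was finalized before database lock at version 1.3 and version 1.6 records changes from the review process, anything added now must be labelled post hoc.

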### 5.3.2 Additional patient reported functional outcomes

1. The difference between the groups in the LEFS.
2. The difference between self-reported pain score at rest, during sitting and during walking in the groups (subset of the PHAT score).
3. Difference between the groups in the percentage of patients that report that they have returned to preinjury sporting activities.
4. Difference in VAS Satisfaction of treatment.
5. Difference in VAS self-reported recovery
6. Difference in in activity level measured by IPAQ short

Endpoints 1, 2, 4, and 5 in the list above will be analyzed in linear regression models analogously to the analysis of the primary endpoint. Endpoint 3 in the list above will be analyzed in a logistic regression model (adjusted for site, age, sex, and degree of tendon retraction) at each follow-up time point.

### 5.3.3 Hamstring muscle strength

The difference between the two treatment groups in the ratio between the injured and uninjured side of the maximum isometric strength in supine position and isokinetic force during knee flexion and hip extension (see protocol appendix physioprotocol and appendix physioinstruction). We will test for differences in the ratio between the groups using a Wilcoxon test, for ease of interpretation. We may also analyse the difference between the groups in a linear regression model, where the dependent variable will be muscle strength in the injured leg, and the independent variable will be muscle strength in the uninjured leg at baseline and the relevant follow-up timepoint, the muscle strength in the injured leg at baseline, site, age, sex, and degree of tendon retraction.

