### 4.2.2 Secondary

The secondary endpoints can be grouped into

- a) adverse events and complications (measured at 3, 6, 12 and 24 months)
- b) additional patient reported functional outcome scores (measured at baseline (if applicable), 3, 6, 12 and 24 month)
- c) physical performance-based tests (measured at 6, 12 and 24 months) including
  - c1) strength tests and
  - c2) functional tests
  - c3) range of motion
- e) imaging outcomes (measured at 24 month).

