### 5.3.4 Physical performance-based tests

- The difference between the two treatment groups in the mean ratio between the injured and uninjured side of the timed step test.
- The difference between the two treatment groups in the mean ratio between the injured and uninjured side of the single leg hop tests.

These endpoints will be analysed similarly to the analysis for hamstring muscle strength (see Section 5.3.3).

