### 5.3.5 Radiological outcomes

- Difference between groups in the ratio of hamstrings muscle volume and fatty infiltration between the injured and uninjured side measured by MRI at 24 months.
- Ratio of attached tendons at the ischial tuberosity measured by MRI at 24 months.

These endpoints will be analysed similarly to the analysis for hamstring muscle strength (see Section 5.3.3).

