## 5.7 Missing data

All reasonable efforts will be taken to ensure that the level of missing data and loss to follow-up will be minimal.

Missing data can occur in different ways in the study: (1) individual questions in the instruments (e.g. the PHAT questionnaire) can be left unanswered; (2) data on specific endpoints may be entirely missing at different follow-up timepoints (due to a e.g. a functional test not being performed or data on a specific instrument not collected); and (3) patients can miss specific follow-up visits or drop out of the study altogether (resulting in no information on endpoint data for the corresponding follow-up timepoint or missing data on all subsequent follow-up timepoints).

Missing data on individual instrument (e.g. PHAT) questions will be imputed using predictive mean matching (PMM), with donor pool (k)=5.

Missed follow-up visit at specific follow-up timepoints will be handled using a multiple imputation by chained equations (MICE). The multiple imputation protocol will be based on models for predicting outcomes at specific follow-up timepoints based on outcomes data recorded at other time points together with treatment group, patient age, sex and degree of tendon retraction. For example, a missing PHAT score at 24 months will be imputed based on a regression model fit to

data from timepoints 3, 6, and 12 together with treatment group, patient age, sex and degree of tendon retraction.

We will generate 1,000 datasets with imputed outcome data, which will be analyzed separately. We will then use Rubin's rules to pool the estimated absolute differences in PHAT score and standard errors.

The global COVID pandemic has occurred during the conduct of this trial. COVID and restrictions have had a major impact on the healthcare situation and has resulted in rescheduled and cancelled follow-up visits in PHACT. Therefore, visits will be analyzed as follows:

- Visits occurring 2.5 to 4.5 months after randomization (or baseline for the observational cohort) will be considered as the 3 month visit.
- Visits occurring 4.5 to 9 months after randomization (or baseline for the observational cohort) will be considered as the 6 month visit.
- Visits occurring 9 to 18 months after randomization (or baseline for the observational cohort) will be considered as the 12 month visit.

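### The strength, function, range-of-motion and MRI ratios have only an unadjusted Wilcoxon test committed, with no effect estimate, no interval and no model to carry the per-protocol weights

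*SAP*

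**What the plan says.** SAP 5.3.3 takes the injured-to-uninjured ratio of muscle strength as the endpoint and states: "We will test for differences in the ratio between the groups using a Wilcoxon test, for ease of interpretation". Sections 5.3.4 (step and hop tests), 5.3.5 Range of motion and 5.3.5 Radiological outcomes each refer back to 5.3.3 for their method. No covariates, weights, effect estimate or interval are attached to the test.

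The next sentence of 5.3.3 adds an option, with strength on the injured side as the outcome: "We may also analyse the difference between the groups in a linear regression model, where the dependent variable will be muscle strength in the injured" … Its independent variables are uninjured-leg strength at baseline and at follow-up, then "the muscle strength in the injured leg at baseline, site, age, sex, and degree of tendon retraction".

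Four other places bear on this:
- 5.1 estimates per-protocol contrasts with inverse-probability weights, "using marginal models with a robust (sandwich) standard error estimator according to models specified in Sections 5.2 and 5.3". The as-treated analysis reuses these weights.
- 5.3.4 defines the first functional endpoint as "The difference between the two treatment groups in the mean ratio between the injured and uninjured side of the timed step test", and the hop tests in the same way.
- 5.7 imputes missed visits by chained equations and uses Rubin's "rules to pool the estimated absolute differences in PHAT score and standard errors".
- 5.3.5 Radiological outcomes includes "Ratio of attached tendons at the ischial tuberosity measured by MRI at 24 months".

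On timing, 4.2.2 lists "physical performance-based tests (measured at 6, 12 and 24 months) including" strength, function and range of motion, and puts imaging at 24 months only.

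**The concern.** Every patient-reported outcome in 5.2 and 5.3.2 that has a named method gets a covariate-adjusted regression. The ratio endpoints get a rank test and nothing else that is binding. A reader is promised a p-value but no size of difference between arms, although the reason given for the choice is interpretability.

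The per-protocol analysis adds a second problem. Section 5.1 itself says that this population may give biased results and makes weighting the remedy. For these endpoints 5.3 commits to no model to which the weights could be applied, so an analyst who follows the text would run an unweighted, unadjusted comparison in a selected set.

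The strength and functional tests matter because 4.3 has them done by a physiotherapist blinded to treatment, whereas the primary endpoint is self-reported. A usable estimate from them would be informative beside PHAT.

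**Working it through.** There is no stated figure to reproduce, so the check begins with the text.

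**1. What other sections need, against what the Wilcoxon test supplies as specified**

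| Need | Supplied |
|---|---|
| 5.1: weighted marginal model with sandwich standard error | No model, no weights |
| 5.3.4: difference in mean ratio (step, hop) | A test on ranks, no estimate |
| 5.7: estimate and standard error to pool (stated for PHAT) | Neither, and no other rule given |
| 5.3.5 Radiological: attached tendons | A p-value, not how many patients have tendons attached |

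On the last row: 5.5.2 names two tendon units. If the ratio is attached units over two (an assumption), it can only be 0, 0.5 or 1.

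**2. Does the optional regression fill the gap?** No, for four reasons:
- It is something the analysts may do, not will do.
- Its list of independent variables does not include treatment arm.
- Its outcome is injured-leg strength, not the ratio.
- It needs baseline strength of both legs, but 4.2.2 schedules these tests at 6, 12 and 24 months. For MRI there is no earlier measurement at all. It cannot be fitted as written.

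**3. Rank test against difference in means.** Assumed inputs: 60 per arm; both arms have mean ratio 0.85; one arm is normal with SD 0.15, the other is left-skewed as 0.85 − 0.10 × (L − 1.499), with L lognormal and median 1. The skewed arm's median is 0.85 + 0.10 × 0.499 = 0.90. In 5,000 simulated trials at two-sided 5%, Wilcoxon rejected in 15.7% and the Welch test of means in 6.0%. The two tests address different targets.

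**4. Unweighted test in the per-protocol set, adherence driven by retraction in one arm.** Assumed inputs: no treatment effect; 60 per arm (SAP 6.2); half the patients have large retraction, which lowers the ratio by 0.15; residual SD 0.15; operative adherence 0.95 throughout; non-operative adherence pL (large retraction) and pS (small retraction).

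The share with large retraction among non-operative adherers is pL/(pL + pS), against 0.5 in the operative arm. The expected spurious difference is 0.15 × (0.5 − share).

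| pL / pS | Share | Expected difference | Simulated, unweighted | Simulated, weighted | Wilcoxon rejects |
|---|---|---|---|---|---|
| 0.70 / 0.85 | 0.452 | 0.007 | 0.006 | −0.001 | 5.8% |
| 0.60 / 0.90 | 0.400 | 0.015 | 0.016 | 0.001 | 7.3% |
| 0.50 / 0.95 | 0.345 | 0.023 | 0.024 | 0.000 | 10.8% |

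Each row has 3,000 trials, so the simulation error at 5% is √(0.05 × 0.95/3000) = 0.4 points. The first row is barely distinguishable from nominal.

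**5. A wider set of assumptions.** No treatment effect; 60 per arm; 10–20% non-adherence; log-odds of non-adherence 0.5–1.5 per SD of retraction; correlation of retraction with the ratio −0.3 to −0.5; 12 scenarios of 2,000 trials.

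| Analysis at nominal 5% | Rejection |
|---|---|
| Wilcoxon, ITT | 4.4–5.8% |
| Wilcoxon, per-protocol, same direction in both arms | 4.4–6.0% |
| Wilcoxon, per-protocol, non-operative arm only | 4.4–8.4% |
| Wilcoxon, per-protocol, opposite directions | 5.3–19.0% |
| Regression on arm and retraction, per-protocol, opposite directions | 4.3–6.3% |

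Repeat runs put the worst opposite-direction case at 18.4% and 19.7%. At log-odds 1, correlation −0.5 and 20% non-adherence it was 12.6%.

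**The case against.** The best defence is that the main analyses of secondary endpoints compare the randomised groups (5.3), where an unadjusted Wilcoxon test is valid. The ITT row above confirms this. The move to per-protocol in 7.3 names only the primary analysis. This stands, so the bias argument is confined to the per-protocol and as-treated analyses that 5.1 announces.

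Several stronger readings are tempting, and the SAP does not support them:
- *A Wilcoxon test cannot be weighted or pooled.* Weighted rank tests exist, and a rank-based estimate with its standard error can be combined over imputations. The SAP simply specifies none of this.
- *Section 5.7 requires pooling of these endpoints.* The pooling rule is worded for PHAT only. The imputation models draw on other time points, which MRI does not have.
- *Mean ratio is the target throughout.* Only 5.3.4 says so, for step and hop.
- *All these endpoints are read blind.* Section 4.3 covers the physiotherapist's strength and functional tests and says nothing of MRI readers.
- *The false-positive rate is 19%.* That needs retraction to drive non-adherence strongly and in opposite directions in the two arms. None of those inputs is in the SAP. The main per-protocol definition also does not count surgery after 3 months as crossover, which limits non-adherence.

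It may also be said that 7.2 already gives intervals. It does, but within each group and only for MRI volume and fat fraction, so no between-group interval results.

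Finally, the SAP is at version 1.6, after journal review. Replacing the prespecified test now would be a post-hoc change. That is a good reason to add to it rather than displace it.

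**Conclusion.** The point holds as a specification gap in secondary endpoints. For all the ratio endpoints the only binding analysis gives no effect size or interval. For step and hop it does not estimate the stated target. For per-protocol it offers no model to which the 5.1 weights apply. The optional regression does not cure this as written. These conclusions rest on the text alone.

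The size of any per-protocol bias does depend on assumptions: about 4–11% rejection at nominal 5% when retraction drives adherence in one arm, and up to about 19% in the worst opposite-direction case. Leaving out the weights matters only where adherence depends strongly on prognosis. In ITT there is no validity problem, and a preference for means over ranks there is partly a matter of taste. The conclusion on the primary endpoint is unaffected.

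**What to change.** - **Model.** Replace the optional regression in 5.3.3 with a committed linear regression of the same-visit injured/uninjured ratio on treatment arm, age, sex and retraction, with site handled by the rule in 5.8.6 and robust standard errors. Report the difference between arms with a 95% confidence interval. State for range of motion which ratio is meant, since that section does not mention the two legs.
- **Per-protocol.** Fit the same model with the 5.1 weights.
- **Missing data.** Where these outcomes are imputed, pool the arm coefficient by Rubin's rules.
- **Wilcoxon test.** Keep it alongside in ITT.
- **Attached tendons.** Report the proportion with all tendons attached in each arm and the risk difference with a 95% interval.
- **Status.** Label the added estimates as post hoc in section 7, as was done for the relative risks and the limb symmetry index.

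The cost is some SAP wording and a few lines of code. The drawback is that mean ratios are more sensitive to outliers than ranks; the retained Wilcoxon test covers that.
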